10.6.2. Study Procedures During Covid-19 Pandemic

During the special circumstances caused by the current COVID-19 pandemic, you should consider specific public health guidance, the impact of any travel restrictions implemented by local/regional health authorities and local institutions, and individual benefit /risk when making enrolment and treatment decisions for trial participants.

As outlined in Section 8, Protocol waivers or exemptions are not allowed and every effort should be made to adhere to protocol-specified assessments for participants on study intervention, including follow up however when not possible, for the duration of these special circumstances, the following measures may be implemented for enrolled participants.

- Clinical investigators should document in site files and in participant notes as appropriate how restrictions related to COVID-19 led to the changes in study conduct and duration of those changes and indicate which trial participants are impacted and how those trial participants are impacted (as per the current local COVID-19 related regulatory guidance).
- Missing protocol required data/visits due to COVID-19 should be noted in participant notes and recorded as a COVID-19 protocol deviation.

Protocol Defined Procedures/Visits:

- The protocol defined interval for the collection of samples during the follow-up visit (see Section 1.3: Schedule of Activities), may be extended up to a maximum length of 14 days.

Data Management/Monitoring:

- If a situation arises where on-site monitoring is no longer permitted, GSK will consider remote Source Data Verification/Source Document Review (SDV/SDR)

where permitted by the clinical site/institution. Remote SDV/SDR will be proposed to study sites to meet a participant and/or critical quality need, eg, to assess participant safety or to ensure data integrity. In case of remote SDV/SDR, GSK will work with the site to ensure participant privacy.

- eCRF/CRF Final or Interim Sign off Process: The Principal Investigator (PI) is responsible for ensuring that the data within the eCRF casebook and any other data sources utilized during the study for each study participant is complete and consistent with source documents throughout the study (ICH GCP 4.9.1 and 4.9.2). The PI may sign/re-sign the eCRF from any computer/location by accessing InForm (or other eDC platform) using his/her unique eCRF log-in credentials. The PI may delegate this activity to another medically qualified and trained sub-investigator and this must be documented on the Delegation of Responsibilities (DoR) Log. It is recommended that the PI identifies a sub-investigator as a back-up for eCRF signatures. The sub-investigator must be appropriately trained on the protocol and eCRF requirements (with training documented), and the DoR log updated accordingly.
- Essential Document Sign Off Process: If an Investigator is unable to print and sign essential documents such as Protocol /Amendment signature page, then Email approval can be accepted by replying to the relevant email that is sent by GSK.

10.7. Appendix 7: Abbreviations and Trademarks

Abbreviation	Definition
ABRS	Acute bacterial rhinosinusitis
ADE	Adverse Device Effects
AE	Adverse event
ALT	Alanine aminotransferase
AMC	Amoxicillin
AOM	Acute otitis media
ARTI	Acute respiratory tract infection
AST	Aspartate aminotransferase
CABP	Community acquired bacterial pneumonia
CARTI	Community acquired respiratory tract infections
CIOMS	Council for International Organizations of Medical Sciences
CV	Cardiovascular
CVA	Clavulanic acid
eCRF	Electronic case report form
EOT	End of Therapy
ES	Extra strength
FU	Follow up
GCP	Good Clinical Practice
HCP	Healthcare professional
HRT	Hormonal replacement therapy
ICF	Informed consent form
IEC	Independent Ethics Committee
IRB	Institutional Review Board

Abbreviation	Definition
MEE	Middle ear effusion
MIC	Minimum inhibitory concentration
OT	On-therapy
PD	Pharmacodynamics
PDD	Protocol-defined diarrhea
PI	Principal Investigator
PISP	Penicillin-intermediate resistant S. pneumoniae
PK	Pharmacokinetics
PRSP	Penicillin resistance S. pneumoniae
SADE	Serious adverse device effects
SAE	Serious adverse events
SoA	Schedule of Activities
SUSAR	Suspected unexpected serious adverse reactions
TEAE	Treatment-emergent adverse events
TM	Tympanic membrane

Trademark Information

Trademarks of the GlaxoSmithKline group of companies	Trademarks not owned by the GlaxoSmithKline group of companies
None	Chiron RIBA SAS WinNonlin

## MODIFICATION HISTORY

Unique Identifier for this Version	Date of the Document Version	Author	Significant Changes from Previous Authorized Version
1.0	18JUL2022	PPD	Not Applicable – First Version

Document:	W:\eedrc-vnasc01\RIOS\data\GSKIBRI_250001	PPD	Biostatistics\Documentation\SAP
Author:			Version Number: V1.0
			Version Date: 18JUL2022
Template No.:	CS_TP_BS016	Revision 6	Reference: CS_WI_BS005

Effective Date: 02Dec2019

## ABBREVIATIONS

AE	Adverse Event
ABRS	Acute bacterial rhinosinusitis
ALT	Alanine aminotransferase
AMC	Amoxicillin
AOM	Acute otitis media
ARTI	Acute Respiratory Tract Infections
AST	Aspartate aminotransferase
ATC	Anatomical Therapeutic Class
CABP	Community-Acquired Bacterial Pneumonia
CI	Confidence Interval
CTMS	Clinical Trial Management System
CVA	Clavulanic acid
DMC	Data Monitoring Committee
ECG	Electrocardiogram
EOT	End of Treatment
ENR	Enrolled Population
FU	Follow Up
ES	Extra Strength
ITT	Intent-To-Treat
MEdDRA	Medical Dictionary for Regulatory Activities

Document: \\ieedc-vnasc01\BIOSdata\GSK\BRL25000\PPD Biostatistics\Documentation\SAP  
Author: PPD Version Number: V1.0  
Version Date: 18JUL2022

Template No.: CS\_TP\_BS016 Revision 6

Reference: CS\_WI\_BS005

Effective Date: 02Dec2019

OT	On Therapy
PT	Preferred term
PDD	Protocol Defined Diarrhea
SAE	Serious Adverse Event
SAP	Statistical Analysis Plan
SOC	System Organ Class
TEAE	Treatment Emergent Adverse Event
WHO	World Health Organization
WHO-DD	WHO Drug Dictionary

## 1. INTRODUCTION

This document describes the rules and conventions to be used in the presentation and analysis of safety and clinical efficacy data for Protocol 213514. It describes the data to be summarized and analyzed, including specifics of the statistical analyses to be performed.

This statistical analysis plan (SAP) is based on protocol version 1.0 amendment 01 dated 19May2021.

## 2. STUDY OBJECTIVES, ENDPOINTS AND ESTIMANDS

### 2.1. PRIMARY AND SECONDARY OBJECTIVE

Table 1

Objectives	Endpoints
Primary	Primary

The primary objective of the study is to assess treatment-emergent adverse events (TEAEs) in children receiving Augmentin (ES)-600 (AMC/CVA 14:1) at 90/6.4 mg/kg/day in two divided doses, administered for 10 days in ARTIs(AOM, ABRS or CABP).

	

Safety will be evaluated by assessing the incidences of treatment emergent adverse events (TEAE).

Secondary	
Secondary
 

The secondary objective of the study is to assess clinical efficacy and incidence of protocol defined diarrhoea (PDD) in children receiving Augmentin (ES)-600 AMC/CVA 14:1 at 90/6.4 mg/kg/day in two divided doses administered for 10 days in ARTIs (AOM, ABRS or CABP).

Efficacy assessment will be based on:

1. Early clinical response at the on-therapy visit (Day 3 to 5), defined in terms of 'success' or 'failure' to study intervention.

2. Primary clinical response at the end-of-therapy visit (Day 12 to 14), defined in terms of 'success' or

Document: \\ieedc-vnasc01\BIOSdata\GSK\BRL25000 PPD  
Author: PPD

\Biostatistics\Documentation\SAP

Version Number: V1.0

Version Date: 18JUL2022

Reference: CS\_WI\_BS005

Template No.: CS\_TP\_BS016 Revision 6

Effective Date: 02Dec2019

	
‘failure’ to study intervention
 
3. Secondary clinical response at follow-up (day 22 to 28) i.e., ‘success’ or ‘failure’.
 

• Incidence of protocol-defined diarrhea (PDD) in children receiving Augmentin (ES)-600 (AMC/CVA 14:1) at 90/6.4 mg/kg/day in two divided doses administered for 10 days in ARTIs (AOM, ABRS or CABP).

--	---

## 2.2. ESTIMANDS

The primary, and secondary estimands to support regulatory decisions are described in following table:

Primary Estimand: -

The primary clinical question of interest is:

To assess treatment-emergent adverse events (TEAEs) in children receiving Augmentin (ES)-600 (AMC/CVA 14:1) at 90/6.4 mg/kg/day in two divided doses, administered for 10 days in ARTIs (AOM, ABRS or CABP).

The primary estimand is described by the following attributes:

- Population:  
Children with acute respiratory tract infections (ARTIs) in India between 6 months to 12 years of either gender
- Treatment conditions:  
Augmentin (ES)-600 with dose level 90/6.4 mg/kg/day twice daily (12 hourly) for 10 days.
- Variables/Endpoints:  
Treatment emergent adverse events (TEAEs), Serious treatment emergent adverse events (TESAEs).
- Summary measure:

Document: \\ieedc-vnasc01\BIOSdata\GSK\BRL25000\PPD\Biostatistics\Documentation\SAP  
Author: PPD

Version Number: V1.0

Version Date: 18JUL2022

Template No.: CS\_TP\_BS016 Revision 6

Reference: CS\_WI\_BS005

Effective Date: 02Dec2019

Counts and percentages for incidence of TEAEs and TESAEs, 95% CI for subjects who have at least one or Any TEAE.

- Intercurrent events (ICEs):  
Discontinuation of study treatment due to any reason – While-on-treatment strategy for TEAEs and TESAEs.

Rationale for Estimand:

The rationale of the while-on-treatment strategy is to estimate the occurrence of TEAEs and TESAEs when subjects have taken the dose/treatment condition.

Treatment Policy will be used for post-treatment AEs, Pre- and Post- treatment SAEs.

The reasoning of treatment policy (as collected) is to estimate the occurrence of post-treatment AEs, and pre- and post-treatment SAEs until subjects are on study will be collected and reported.

No intercurrent event is defined for other safety endpoints. The data will be analyzed as collected.

Secondary Estimands :-

The secondary clinical questions of interest are:

To assess Early and Primary responses in children receiving Augmentin (ES)-600 (AMC/CVA 14:1) at 90/6.4 mg/kg/day in two divided doses administered for 10 days in ARTIs (AOM, ABRS or CABP).

The secondary estimands are described by the following attributes:

1. Early clinical response at on-therapy [(OT) (Day 3 to 5)]
  - Population:  
Children with acute respiratory tract infections (ARTIs) in India between 6 months to 12 years of either gender.
  - Treatment conditions:  
Augmentin (ES)-600 with dose level 90/6.4 mg/kg/day twice daily (12 hourly) for 10 days.
  - Variable/Endpoint:  
Proportion of successful early clinical response at on-therapy (OT) visit.
  - Summary measure:  
Counts and percentages for early clinical response at on-therapy (OT) visit with corresponding 95%CI.
  - Intercurrent events (ICEs):

Document: \\ieedc-vnasc01\BIOSdata\GSK\BRL25000\PPD\Biostatistics\Documentation\SAP

Author: PPD

Version Number: V1.0

Version Date: 18JUL2022

Template No.: CS\_TP\_BS016 Revision 6

Reference: CS\_WI\_BS005

Effective Date: 02Dec2019

- Discontinuation of study treatment due to AE, discontinuation of study treatment due to lack of efficacy and use of rescue medication - Composite strategy

If subject discontinue due to above mentioned ICEs, then early response for that subject will be imputed as a failure.

- Discontinuation of study treatment due to any other reason – Treatment Policy

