9.4.3. Secondary Endpoint(s)

Statistical analyses on efficacy endpoints will be conducted using participants from the Intent to treat population. All the displays will be created as overall summaries and as stratified by indication.

Early Clinical Response

The estimand is the proportion of successful clinical responses. The intercurrent events expected for this endpoint are:

- Discontinuation of study treatment due to AE
- Discontinuation of study treatment due to lack of efficacy
- Use of rescue medication
- Discontinuation of study treatment due to any other reason

The estimand strategies for the above intercurrent events are

- A **composite strategy** would be used if intercurrent event '**Discontinuation of study treatment due to AE**' **Discontinuation of study treatment due to lack of efficacy**' and '**Use of rescue medication**' occur. That is, if a subject discontinues the study treatment due to AE or due to lack of efficacy or uses rescue medication, the subject will be imputed as a failure.
- A treatment policy would be used if intercurrent event 'Discontinuation of study treatment due to any other reason' occurs. That is, if a subject discontinues the study treatment due to any other reason (other than AE, lack of efficacy or use of rescue medication), the data for that subject will be analysed as collected

The proportion of clinical response OT (Days 3 to 5) (defined as: A treatment success is defined as either "clinical cure" or "improvement" at end of therapy and treatment failure is defined as a participant whose clinical outcome was "clinical failure" or "unable to determine") with corresponding 95% CI will be calculated. A full description of statistical analysis methods will be mentioned in SAP of study.

Primary Clinical Response

The estimand is the proportion of successful clinical responses. The intercurrent events expected for this endpoint are:

- Lack of compliance (<80%)
- Discontinuation of study treatment due to lack of efficacy
- Discontinuation of study treatment due to AE
- Use of rescue medication
- Discontinuation of study treatment due to any other reason

The estimand strategies for the above intercurrent events are

- A **principal stratum** strategy will be used in case of '**Lack of compliance (<80%)**'. That is, only those subjects who have more than 80% compliance would be considered in the calculation of proportion.

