#### Rationale for estimand:

Discontinuation of study treatment due to AE, discontinuation of study treatment due to lack of efficacy and use of rescue medication will affect the early clinical response thus the early clinical response will be counted as failure under composite strategy.

The reasoning of treatment policy is to estimate the early clinical response until subjects are on study will be collected and reported (regardless of the intercurrent event occurring).

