## 6.6. WINDOWING CONVENTIONS

The following visit window will be used for efficacy as well as safety assessment.

Visit	Target Days	Visit Window
Baseline	0	Prior to first dose of study medication
Visit 1	1	#1
On-therapy visit or OT visit	3	2-5
End of therapy visit or EOT visit	12	6-14
Interim visit recurrence	18	15-21
Follow-up visit	25	$\geq 22$

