# Visit 1 will be considered as baseline for patient diary card assessments if subject does not have patient diary data prior to Visit 1.

\* Interim visit (< 24 hrs of notification) is required only if subject having clinical failure or PDD or server AE of SAE after OT visit prior to EOT visit. In this case all assessment of interim visit will be mapped to EOT visit as scheduled.

If there is more than one record for a given parameter within a specific visit window, then the non-missing record closest to the target day will be summarized. If there are multiple records on the same day for a parameter, then the average value will be considered for continuous parameters, and the worst value will be considered for the categorical parameters.

Study treatment discontinuation and unscheduled visit will also be considered for deriving the visit window for parameters.

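### The composite rule for early clinical response has no time limit: read literally it recodes a Day 3-5 success as a failure after a later stop, while the SAP 15.1 formula does not

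*SAP*

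**What the plan says.** SAP 2.2 defines the early-response variable as "Proportion of successful early clinical response at on-therapy (OT) visit", with treatment given "twice daily (12 hourly) for 10 days". It lists three intercurrent events under a composite strategy: stopping for an AE, stopping for lack of efficacy, and use of rescue medication. The rule follows: "If subject discontinue due to above mentioned ICEs, then early response for that subject will be imputed as a failure". The rationale beneath it says that these events "will affect the early clinical response thus the early clinical response will be counted as failure under composite strategy".

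Protocol 9.4.3 counts the child as a failure "if a subject discontinues the study treatment due to AE or due to lack of efficacy or uses rescue medication". This wording reaches rescue use without a stop. The SAP's imputation sentence speaks only of subjects who discontinue, although its list and rationale include rescue use. Neither text attaches a date, visit or window to the event.

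SAP 15.1 then gives the calculation: children categorised as cured or improved at the OT visit, divided by the ITT population. It does not mention the composite.

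**The concern.** Early response is fixed once the OT visit is over. Treatment continues after that, and both documents provide for what happens next: Protocol 4.1 and SAP 3.1 describe an interim visit, with withdrawal from study treatment at the investigator's discretion, for clinical failure, protocol-defined diarrhoea, a severe AE or an SAE between OT and end of therapy (EOT). If the recorded reason for stopping is an AE or lack of efficacy, such a child meets the composite rule as written. A valid, already observed success would then be overwritten by an event that could not have influenced it.

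Two things are at stake. The early-response estimate could be lower than the response seen at Day 3 to 5. And two programmers could follow different sections of the same SAP and report different numbers, overall and by indication.

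**Working it through.** **1. Is there a time limit anywhere?**

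| Place | What it supplies |
|---|---|
| SAP 2.2 and Protocol 9.4.3, composite rule | No limit |
| SAP 2.2, rationale | Says the events affect early response; does not say when they must occur |
| SAP 6.6, window table | The row "On-therapy visit or OT visit" covers Days 2-5 and EOT covers Days 6-14; these windows place assessments, not intercurrent events |
| SAP 6.6, note on the interim visit | "In this case all assessment of interim visit will be mapped to EOT visit as scheduled"; again about assessments |
| SAP 3.3 and 7.3 | No change from protocol; missing data not imputed; no limit added |

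**2. One child, two codings.** Take a child who is cured at the OT visit and stops for an AE on Day 9.
- Under SAP 2.2 or Protocol 9.4.3: early failure.
- Under SAP 15.1: early success.
- For primary (EOT) response, SAP 2.2 makes the child a failure if compliance is at least 80%. With 18 doses over 9 days, the SAP 14.1 formula gives 18/(9 × 2) = 100%. So under the literal rule one late event counts in both endpoints.

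**3. The plan's own precision figure.** The documents state precision only for the proportion with a TEAE: ±5.43 points at 37.9% and n = 310, interval 32.5% to 43.3%. The Wald formula gives 1.96 × √(0.379 × 0.621/310) = 5.40 points and the same interval to one decimal. No figure is given for early response, and nothing below rests on this one.

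**4. Effect per child.** Each OT success recoded lowers the proportion by 1/n. The sample sizes are those in Protocol 9.2 and SAP 6.8.
- Overall: 1/310 = 0.32 points
- AOM: 1/136 = 0.74 points
- ABRS: 1/106 = 0.94 points
- CABP: 1/68 = 1.47 points

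**5. Effect over an assumed range.** The documents give neither an early success rate nor a rate of later events among early successes. Assume 90% success at OT, 279/310, with exact (Clopper-Pearson) 95% CI 86.1% to 93.1%, a half-width of 3.5 points. Let k be the number of OT successes with a later listed event.

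| Assumed share of 310 | k | Literal rule, (279 − k)/310 | Exact 95% CI | Shift, k/310 |
|---|---|---|---|---|
| 1% | 3 | 89.0% | 85.0 to 92.3 | 1.0 |
| 2% | 6 | 88.1% | 83.9 to 91.5 | 1.9 |
| 3% | 9 | 87.1% | 82.8 to 90.6 | 2.9 |
| 5% | 16 | 84.8% | 80.4 to 88.6 | 5.2 |

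The shift in points does not depend on the 90%: starting from 85% or 95% gives the same last column. It reaches the half-width of the interval at about 11 children (11/310 = 3.5 points).

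**The case against.** The strongest reply is that a limit was plainly intended. The variable is response at the OT visit. The rationale justifies the composite because the events affect early response, which a Day 9 stop cannot do. Problems between OT and EOT are evaluated as primary response, and the interim visit is mapped to EOT. The calculation in SAP 15.1 uses the OT categorisation alone. On this view the documents need a clarification and no child would in fact be recoded.

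Much of this stands. It shows that recoding is one reading and not a certainty, and that the likely intention agrees with the fix. It does not remove the problem, because the intention has to be inferred while the rule is stated twice without a limit. Nor can SAP 15.1 simply be taken as governing: it omits the composite altogether, including for a child who stops before the OT visit.

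It is also fair to say that the size is assumed. Protocol 7.1 describes permanent discontinuation as rare, and 7.2 describes withdrawal as uncommon. The pathway in Protocol 4.1 is a contingency, not a forecast. A reader might reach for a 10% scenario, or for the 11% diarrhoea rate that Protocol 2.2 reports for the high dose. The documents do not support either as a rate here: the 11% is total incidence in another study, not later stopping among children who had already responded.

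**Conclusion.** The point holds as a missing time limit and a conflict within the SAP. SAP 2.2 and Protocol 9.4.3, applied as written, turn an observed OT success into an early failure after a later stop (or, under the protocol wording, later rescue use); SAP 15.1 leaves it a success. If the literal rule is followed, the bias can only be downward and equals the share of the ITT population who were OT successes and then had a listed event. On an assumed 1% to 5%, that is about 1 to 5 points overall, with each child weighing most in CABP.

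A reader might go further and infer that early response stops being distinct from the EOT endpoint, or becomes a measure of tolerability over Days 6 to 14. The documents do not support that. Even on the literal reading, every child without such an event is scored on the OT assessment, and the EOT endpoint uses a different assessment and a compliance restriction. A 10-day course also leaves no room for stopping treatment early on Days 11 to 14. The two endpoints would partly overlap, no more.

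The consequence is moderate. The endpoint is secondary and descriptive in a single-arm study with no formal hypothesis, and the primary TEAE endpoint is untouched. The correction is worth making because it is nearly free.

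**What to change.** 1. In SAP 2.2 and Protocol 9.4.3, limit the composite for early response to the listed intercurrent events that occur *on or before the date of the OT assessment, including a stop decided at that visit*. State that later events count only toward primary (EOT) response. The stop decided at OT needs naming because Protocol 4.1 and SAP 3.1 treat that visit as EOT. Say also which date is the event date, for example the decision to stop and not the last dose.
2. Write the same rule into the early-response formula in SAP 15.1, so that definition and calculation agree.
3. Keep the plan's own intercurrent-event terms in this change. Separately, reconcile the use of rescue medication as an intercurrent event with Protocol 6.5.1, which lists rescue medicine as not applicable, and align the SAP's imputation sentence with the protocol on rescue use without a stop.
4. Correct the Protocol 9.4.3 definition of OT success, which places cure or improvement at the end of therapy.

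The cost is one clause in each of three places, two small wording corrections, and one date condition in the program. Sample size and visit schedule do not change.
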